#### 5.7.11. Missing Start Date, Stop Date, Severity, or Relationship for Adverse Events

The same conventions to address incomplete dates for prior and concomitant medications will also be used for AEs. Should an event have a missing severity or relationship, it will be classified as having the highest severity and/or strongest relationship to study treatment.

#### 5.7.12. Windowing and Multiple Lab Values

Unscheduled and early termination visits will be assigned to an analysis window according to the study day of the actual visit date using visit windows described in Table 3 below:

Visit	Relative Target Day	Analysis Visit Window
Screening (optional)	-35 to -1	Prior to Day 1
Day 1 (Baseline)	1	1
Week 4	29	2 to 43
Weeks 8 to 92	Week * 7 +1	Target Day -13 to Target Day +14
Week 96	673	660 to 701
Week 104 to 136	Week * 7 +1	Target Day -27 to Target Day +28
Week 144	1009	982 and later

Table 3:Visit Windows

For subjects with multiple lab values on the same day, special rules will be used to choose values eligible for display on tables and figures. For South African sites: on days with multiple test results, results from the local lab will be used. For other sites: on days with multiple test results, results from the central lab will be used. If there are still multiple records on the same date, then the median of available records on that date will be used; for these created median records, if applicable, the most frequent toxicity grade of the records used to calculate the median will be used.

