5.4. Clinical Findings for BCX9930

[figure not shown]
The safety and effectiveness of BCX9930 in PNH was initially evaluated in the Phase 1, three-part, first-in-human (FIH) Study BCX9930-101 (Study 101). In Part 3 of Study 101 a total of 16 subjects with PNH were enrolled. This study, BCX9930-201 (Study 201) is a long-term rollover study for all PNH subjects who previously received BCX9930 in Study 101 Part 3 and derived benefit from BCX9930 treatment. Fifteen subjects from Study 101 Part 3 enrolled into this study. [REDACTED]

[REDACTED]

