A subject may be enrolled once all eligibility criteria and study requirements are met. On-treatment study visits will occur on Day 1, then every 4 weeks up to Week 96 and then every 8 weeks until Week 144. Subjects with sCr elevations will be required to complete additional assessments at the investigational site, at a laboratory local to the subject, or via a home health service (where permitted and available) as indicated in [Section 11.3.4.1](#) and [Section 13.9.5.3](#). An independent DMC will continue to review the safety data from this study in concert with the accumulating safety information generated across the BCX9930 clinical development program. The DMC convened and reviewed safety data once the first 4 subjects enrolled completed 12 weeks of dosing. Subsequent DMC meetings were and will be convened as detailed in the DMC Charter.

Up to approximately 200 subjects may be enrolled into the study. Subjects will be eligible to receive BCX9930 for up to 144 weeks, or until drug is available by another mechanism (eg, expanded or market access) or until the Sponsor discontinues development of the product for PNH; whichever comes first.

A study schema is shown in [Figure 2](#).

Figure 2: Study Schema

Abbreviations: EOT = end of treatment; Wk = week.

^a Subjects with sCr elevations will be required to complete additional assessments to monitor for potential renal toxicity at the investigational site, at a remote laboratory more convenient for the subject, or via a home health service (where permitted and available) as indicated in [Section 11.3.4.1](#) and [Section 13.9.5.3](#).

^b Following discontinuation of study drug, either following completion of the treatment period or on premature discontinuation, subjects will return to the clinic for a minimum of 3 consecutive days to monitor for the onset of hemolysis.

^c Subjects will return to the clinic 3 weeks (21 ± 3 days) after the date of their last dose of BCX9930 for their end of study assessments.

Safety and tolerability will be evaluated through assessments of TEAEs, laboratory analyses (clinical chemistry, hematology, coagulation, and urinalysis), vital signs, ECGs, and physical examinations at the study visits indicated in the schedule of assessments (see [Table 4](#)).

Disease-specific assessments will be performed at study visits as indicated in the schedule of assessments (see [Table 4](#)).

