8.3. Subject Withdrawal Criteria

Participation in the study is strictly voluntary. Subjects have the right to withdraw from study drug or from the study at any time and for any reason. A subject's participation may be terminated for any of the reasons delineated in Section 7.4. Whenever possible, the Investigator will consult with the Sponsor Medical Monitor before halting a subject's participation in the study.

In all cases, the reason for withdrawal from study drug must be recorded in the subject's medical records (source documents). If the reason is not known, the subject must be followed to establish whether the reason was due to an AE, and if so, this must be reported in accordance with the procedures outlined in Section 7.4.1 and Section 13.9.3. Vigorous attempts will be made for follow-up of all subjects who miss a study visit. In general, although study drug may be stopped, subjects will be strongly encouraged to continue to complete the scheduled study visits for hemolysis monitoring (see Section 11.3.5). If the subject is withdrawn from the study prior to scheduled study completion, an early termination visit to complete all end-of-study evaluations will be required. If a subject's participation in this study is terminated, the responsible Investigator/clinical staff member will document termination in the source documents.

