11.3.7. End of Study Visit

Subjects who permanently discontinue treatment will return to the clinic for the hemolysis monitoring visits detailed in Section 11.3.5. Subsequently they will return to the clinic 3 weeks (21 ± 3 days) after the date of their last dose of BCX9930 for their end-of-study assessments.

The following assessments will be performed at the end of study visit:

- Subject weight
- Targeted physical examination
- Vital signs (BP, temperature, and pulse rate)
- 12-lead ECG
- Blood collection for clinical chemistry, hematology, coagulation
- Urine collection for urinalysis with microscopy, urine pregnancy test for female subjects of childbearing potential
- Urine collection for biomarker testing
- Disease-specific assessments:
 - Assessment of PNH symptoms (fatigue, dyspnea, chest pain/discomfort, difficulty swallowing (esophageal pain), abdominal pain, headache, erectile dysfunction, hemoglobinuria, jaundice)
 - Review of blood transfusions
- PD blood sample
- Review of concomitant medications and AEs
- Study drug accountability (for early withdrawal visit only)

If an AE is ongoing at the end-of-study visit, additional clinic visit(s) or telephone contact(s) may be warranted (see Section 13.9.3).

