13.7. Monitoring for Hemolysis at Discontinuation of BCX9930

By inhibiting the alternative pathway of complement, the factor D inhibitor BCX9930 may improve hemoglobin levels by reducing the hemolysis of PNH RBCs. Thus, following discontinuation of BCX9930 treatment, subjects may be at risk of serious hemolysis.

Based on available data regarding the PK and PD of BCX9930, serious hemolysis, if it occurs, would be expected to present within days after discontinuation of therapy, therefore when subjects stop study drug therapy, either at the scheduled end of treatment or on premature discontinuation, they must be monitored for hemolysis, as described below. Samples may be analyzed at a local laboratory.

Hemolysis will be monitored by daily laboratory assessment of LDH, hemoglobin, complete blood count (CBC), and serum chemistry (serum creatinine, blood urea nitrogen [BUN]), along with vital signs and a targeted physical examination, for at least 3 consecutive days after discontinuing BCX9930. Sample(s) for PD biomarker analysis and PK will be collected 48 hours after the last dose of BCX9930.

Following the 3 days of monitoring, additional laboratory monitoring may be necessary, based upon the safety assessment of the Investigator and the Sponsor Medical Monitor.

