## 3.7. Clinical Assessments

Planned study visits are Screening; Day 1; Weeks 4 through 96 at 4-week intervals, and Weeks 104 through 144 at 8-week intervals. Safety and tolerability will be evaluated through assessments of TEAEs, laboratory analyses (clinical chemistry, hematology, coagulation, and urinalysis), vital signs, ECGs, and physical examinations at the study visits indicated in the schedule of assessments (see Table 2).

- The questionnaires are to be administered first, then physical exam, then ECG and vital signs before lab samples, PNH clone sample, then PK, PD, concomitant medication and AE review, PNH symptoms assessment, transfusion review, and finally drug dispensing.
- A site is permitted to perform screening assessments over more than one screening visit. Rescreening of ineligible subjects will be approved or denied on a case-by-case basis by the Sponsor Medical Monitor. Retesting of specific assessments without entirely rescreening a subject may be permitted. A screening failure electronic case report form (eCRF) page will be completed for those subjects who do not proceed with study dosing.
- Subjects who dose escalate (under Protocol versions 1-3) will have an additional Dose Escalation visit 2 weeks (± 2 days) after each dose increase.
- Following discontinuation of study drug (either following completion of the treatment period or on premature discontinuation), subjects will return to the clinic for a minimum of 3 consecutive days for Hemolysis Monitoring visits. Following the 3 days of monitoring, if required, subjects may continue to be assessed every 2 days thereafter until the subject has stabilized to a new hemoglobin baseline.
- Subjects who permanently discontinue treatment will return to the clinic for Hemolysis Monitoring visits. Subsequently they will return to the clinic 3 weeks (21 ± 3 days) after the date of their last dose of BCX9930 for their End of Study assessments.

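### SAP 5.7.12 windows early-termination and unscheduled visits by study day with no last-dose limit, so any made after stopping drug count as treatment visits; separately, by-visit percentages default to the whole treatment group

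*SAP*

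**What the plan says.** **Windowing.** SAP 5.7.12 gives one rule: "Unscheduled and early termination visits will be assigned to an analysis window according to the study day of the actual visit date". The Table 3 windows are contiguous from Day 2, and the last one, Week 144, is open-ended from Day 982. No row is set aside for post-treatment data. The only last-dose cut-off I found in the SAP is the Kaplan-Meier censoring in 9.1.1, which does not touch by-visit tables.

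**Visits after stopping.** For a subject withdrawn before scheduled completion, Protocol 8.3 says "an early termination visit to complete all end-of-study evaluations will be required", without saying when. Protocol 11.3.7 covers subjects who permanently discontinue treatment: after hemolysis monitoring, "Subsequently they will return to the clinic 3 weeks (21 ± 3 days) after the date of their last dose of BCX9930". Its assessment list also contains "Study drug accountability (for early withdrawal visit only"), which suggests that an early withdrawal visit may be held at another time. SAP 3.7 adds that after discontinuation "subjects will return to the clinic for a minimum of 3 consecutive days for Hemolysis Monitoring visits". Section 5.7.12 names neither the monitoring visits nor End of Study.

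**Denominator.** SAP 5.4 bases percentages on all subjects in the treatment group unless something else is specified. Sections 8.1.2 (hematological response), 9.2.1 (graded laboratory abnormalities), 9.3 (QTcF categories) and 10.1.1 (PNH symptoms) present percentages by visit or time point and specify nothing else. SAP 5.12.1 imputes no missing data other than dates and times.

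**The concern.** The by-visit tables are meant to show how subjects do on long-term treatment. Protocol 13.7 says that "serious hemolysis, if it occurs, would be expected to present within days after discontinuation of therapy", so a sample taken even a week after the last dose may describe untreated disease. Filed under a treatment week, it distorts the laboratory, vital-sign and symptom rows and the PD rows for Factor Bb and AP Wieslab. The SAP takes care over values distorted by transfusion (5.7.13, 10.1.2) but has no counterpart for values distorted by stopping drug.

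The problem would be concentrated if many subjects stopped together. The protocol provides for that: treatment lasts up to 144 weeks, until drug is available by another route, "or until the Sponsor discontinues development of the product for PNH; whichever comes first".

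The denominator default is a separate matter. With N fixed, a by-visit percentage falls as attendance falls, for good and bad outcomes alike. It matters most at an interim analysis (SAP 4.1), where subjects who have not yet reached a visit still count in N.

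**Working it through.** **Reproducing Table 3.** Target day = 7 × week + 1 gives Day 673 for Week 96 and Day 1009 for Week 144, as stated. This yields 30 post-baseline windows without gaps.

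**Does the receiving window hold an on-drug scheduled visit?** Let L be the last-dose day, k the lag to the early-termination visit, t the latest scheduled target day ≤ L, e the days from target to the upper window edge, and p the visit spacing. Visits are assumed to fall on target days. Day L + k shares t's window only if L − t ≤ e − k. So:

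share without an on-drug scheduled visit = 1 − max(0, e − k + 1)/p

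- Last dose on Days 29-672 (644 days): e = 14, p = 28.
- Last dose on Days 673-1008 (336 days): e = 28, p = 56.

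| Lag k | Days 29-672 | Days 673-1008 |
|---|---|---|
| +7 | 20/28 = 460/644 = 71% | 34/56 = 204/336 = 61% |
| +14 | 27/28 = 621/644 = 96% | 41/56 = 246/336 = 73% |
| +18 | 644/644 = 100% | 45/56 = 270/336 = 80% |
| +21 | 644/644 = 100% | 48/56 = 288/336 = 86% |
| +24 | 644/644 = 100% | 51/56 = 306/336 = 91% |

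Day-by-day enumeration gives the same counts. These are shares of calendar days, not of subjects. At k = 0 the value is itself on drug, so nothing goes wrong.

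Example: last dose at Week 48 (Day 337). A visit at +21 is Day 358, inside the Week 52 window (Days 352-379). At +7 it is Day 344, in the Week 48 window (Days 324-351) together with the on-drug visit. For hemoglobin and the other transfusion-impacted parameters, the closest-to-target rule in 5.7.13 then picks the on-drug value. For other parameters, only same-day duplicates have a selection rule.

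**Weight of one off-drug value.** Among n on-drug values it is 1/(n + 1). Protocol 5.4 reports that "Fifteen subjects from Study 101 Part 3 enrolled into this study". With n = 14 the weight is 1/15 = 6.7%; with n = 199 it is 1/200 = 0.5%. For an assumed off-drug hemoglobin difference of 1 to 3 g/dL, the row mean moves by 0.07-0.20 g/dL and 0.005-0.015 g/dL respectively.

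**If the Sponsor stops development.** Assume last-dose days spread evenly over Days 1-1008 and an early-termination visit for everyone. For a row with target day t, on-drug count = 1009 − t. Off-drug count = number of L < t with L + k in the window.

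| Row | On drug | Off drug, +21 | Share | Off drug, +7 | Share |
|---|---|---|---|---|---|
| Week 48 | 672 | 28 | 4% | 20 | 3% |
| Week 96 | 336 | 34 | 9% | 20 | 6% |
| Week 120 | 168 | 48 | 22% | 34 | 17% |
| Week 136 | 56 | 48 | 46% | 34 | 38% |

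**Denominator.** Displayed % = true % × n/N. At assumed attendance of 90%, 75% and 50%, a true 30% displays as 27%, 22.5% and 15%. At a data cut with the same even spread, 672/1008 = 67% have reached Week 48 and 336/1008 = 33% Week 96, so 30% displays as 20% and 10%. For erectile dysfunction, an assumed male share of 0.4 to 0.6 alone turns 30% of men into 12-18%.

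**The case against.** **The large shares may belong to a different visit.** The 18-24 day lag is that of End of Study, which 5.7.12 does not name and which has its own column in SAP Table 2. Protocol 8.3 ties early termination to withdrawal from the study, which differs from stopping drug. A reader might infer that nearly every discontinuer's off-drug values will be filed as treatment weeks, or that completers' End of Study results will fall into Week 144. The documents do not support either. They give both visits the same content but do not fix the timing of early termination, and they leave windowing of End of Study (completers and premature discontinuers) and of hemolysis monitoring undefined. What stands is the rule for the two visit types that 5.7.12 does name.

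**The denominator may be settled elsewhere.** SAP 5.4 is only a default, SAP 12.2 places display specifications in a separate document, and SAP 5.2 requires tables to show how many subjects the data cover. A fixed N is also an accepted convention, and an observed-case denominator favours those who stay. So it cannot be said that the tables will be wrong. But showing n does not change the stated denominator, and the SAP should settle this itself.

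**The enumeration simplifies the schedule.** The footnote on four-weekly visits counts prior-study weeks toward the 96-week switch. With assumed prior exposure of 12 to 52 weeks, the +7 share rises from 71% to 73-79%, so the simplification does not overstate the problem.

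**Materiality is limited.** No hypothesis is tested (SAP 3.3). Clone size and the three questionnaires are not collected at End of Study. Hematological response is partly protected by its 6-month median, and TEAE incidence is unaffected. At +18 to +24, only 227-233 of 644 last-dose days put the visit in a week with a scheduled ECG. All of this stands and limits the severity.

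**Conclusion.** Both parts hold, within limits.

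1. As written, 5.7.12 reports any early-termination or unscheduled visit made after permanent discontinuation as a treatment visit. How often depends on a timing that the protocol does not give: never for visits on the last-dose day; at +7 days, into a window without an on-drug scheduled visit for 71% and 61% of last-dose days in the two phases; at +18 to +24, for 100% and 80-91%. The effect on a row is minor with many subjects and moderate in late rows with few. The 22% and 46% shares at Weeks 120 and 136 need a programme stop, evenly spread last doses and a +21 visit, all assumed.
2. Unless the display specifications say otherwise, by-visit percentages shrink in proportion to attendance, and erectile dysfunction is divided by both sexes. Continuous summaries are unaffected by this part.

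Neither part systematically flatters the drug. Off-drug hemolysis would tend to worsen late rows, and the denominator lowers favourable and unfavourable categories alike. The case for changing the SAP is that the tables should mean what their row labels say, and the change is cheap.

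**What to change.** **SAP 5.7.12 and Table 3**, add:

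> Assessments made after the last dose before permanent discontinuation, beyond a short pre-specified allowance (e.g. 1 day), do not enter treatment-visit windows, including Week 144. They, and End of Study and hemolysis-monitoring assessments after permanent discontinuation, are summarized in a separate post-treatment row. Assessments during a temporary interruption followed by resumption stay in their study-day window and are flagged.

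The last sentence is needed because Protocol 13.9.5.4 also requires monitoring after an interruption and Protocol 10.5.1 allows resumption. The length of the allowance is an analysis choice; the documents give no figure. Merely closing Week 144 at target + 28 (Day 1037) would not do: after a last dose on Day 1009, monitoring (Days 1010-1012) and End of Study (Days 1027-1033) would still fall inside it.

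Keep post-treatment values, flagged as off drug, in worst-post-baseline and any-occurrence treatment-emergent safety tables, in line with Protocol 14.3.3. In by-visit treatment-emergent tables, show them in the post-treatment row.

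**SAP 5.4**, add:

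> For by-visit percentages the denominator is subjects with a non-missing assessment at that visit (males only for erectile dysfunction), with n printed at each visit.

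**Cost.** Short additions to two SAP sections, one extra row in by-visit tables, some re-programming, and a denominator that changes from visit to visit.

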13.6. Laboratory Assessments

Blood and urine samples will be obtained per the schedule of assessments in [Table 4](#). A list of the laboratory parameters measured is presented in [Table 5](#).

Samples will be collected into appropriate tubes, as specified by the clinical laboratory. All laboratory samples, with the exception of hemolysis testing at study drug discontinuation, will be analyzed by a central laboratory. Local laboratories may be used in place of the central laboratory at the investigator's discretion for logistical reasons (eg, such as delays in transport due to COVID-19), they may also be utilized for analysis of samples collected for assessment of possible AEs. Urine microscopy for samples collected at the investigative site will be performed at the site's local laboratory, where appropriate on-site testing capability exists (see [Section 13.6.1](#)). The additional renal and hepatic safety assessments may be performed at the investigative site or remotely at a location more convenient for the subject or via a home health service. If the use of a home health service is permitted, testing may be performed at the central laboratory or at a remote laboratory. The results from laboratory testing performed at a local or remote laboratory must be provided to the investigational site. Reference ranges for each local laboratory will be provided to the Sponsor and included in data listings. For out-of-range laboratory findings, the interpretation of clinically significant or not clinically significant should be denoted in the source records. Clinically significant laboratory findings in the opinion of the Investigator should be recorded as an AE and handled as described in [Section 13.9](#).

Table 5: Clinical Laboratory Evaluations

Chemistry	Coagulation	

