13.9.5. Toxicity Management

The Investigator (or qualified designee) will grade clinically significant events and laboratory abnormalities (if considered AEs) according to that detailed in Section 13.9.1.5. Grade 3 and 4 clinically significant laboratory abnormalities should be confirmed by repeat testing and before any contemplated study drug/IMP discontinuation, unless such a delay is not consistent with good medical practice.

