## 5.7.13.1. Transfusion-impacted Period for South Africa

The algorithm as defined below aims to exclude transfusion impacted lab measurements when possible, and acts to select local lab measurements over central lab measurements (for South Africa subjects) or central lab measurements over local lab measurements (for subjects outside of South Africa), when possible. This is due to a lack of reliable data obtained from the central lab in South Africa.

For South African sites, the algorithm for determining which values should be used in effectiveness analysis are as follows:

The Hb value to use for a particular visit is provided below. The first item matching the description in the list should be used.

- 1. Local lab value for Hb at the visit of interest closest to the target day.
  - a. If multiple results are equidistant from the target, use the latest.
  - b. If multiple records exist on the same day, find the median of the results on that day (for grading, set to the most frequent grade or worst grade if two grade have the same frequency).
- 2. Central lab value for Hb at the visit of interest closest to the target day.
  - a. If multiple results are equidistant from the target, use the latest.
  - b. If multiple records exist on the same day, find the median of the results on that day (for grading, set to the most frequent grade or worst grade if two grade have the same frequency).

If the value at the visit of interest was taken during a transfusion-impacted period:

- 3. Local lab pre-transfusion value that itself was not within 14 days after the subject received a pRBC or whole blood transfusion.
  - a. If multiple results are equidistant from the target, use the latest.
  - b. If multiple records exist on the same day, find the median of the results on that day (for grading, set to the most frequent grade or worst grade if two grade have the same frequency).
- 4. Central lab pre-transfusion value that itself was not within 14 days after the subject received a pRBC or whole blood transfusion.
  - a. If multiple results are equidistant from the target, use the latest.
  - b. If multiple records exist on the same day, find the median of the results on that day (for grading, set to the most frequent grade or worst grade if two grade have the same frequency).

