## 9.2.1. Analysis of Abnormal Laboratory Values

Laboratory abnormalities will be graded according to DMID Adult Toxicity Table (draft version November 2007, see Protocol Appendix 1), with the exception of creatinine clearance and glomerular filtration rate, which will be graded using the National Cancer Institute (NCI) Common Terminology Criteria for Adverse Events (CTCAE) version 4.03.

Any graded abnormality that occurs following the initiation of study drug and represents at least 1-grade increase from the baseline assessment is defined as treatment emergent. The number and percentage of subjects who experience treatment-emergent graded toxicities will be summarized by panel, parameter, time point, and treatment category. Laboratory toxicity shifts from baseline to worst post-baseline grade will be summarized by panel, parameter, toxicity grade, and treatment.

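### The same-day laboratory rule in SAP 5.7.12 has no exception for worst-grade safety tables, so a Grade 3 or 4 result can drop out of them

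*SAP*

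**What the plan says.** SAP 5.7.12 deals with days on which a subject has more than one result: "special rules will be used to choose values eligible for display on tables and figures". It works in three steps.

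1. Laboratory. Outside South Africa, "on days with multiple test results, results from the central lab will be used"; South African sites use the local laboratory instead.
2. Value. If several records remain, "the median of available records on that date will be used".
3. Grade. For the record so created, where grading applies, "the most frequent toxicity grade of the records used to calculate the median will be used".

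There is no exception for safety tables and no rule for ties. The opening of SAP Section 5 presents its contents as general conventions and leaves data-specific rules to the sections on individual tables.

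SAP 9.2.1 defines a treatment-emergent abnormality as a rise of at least one grade over baseline and adds: "Laboratory toxicity shifts from baseline to worst post-baseline grade will be summarized". It does not say which same-day records enter. SAP 9.2.2 does say so for liver tests: elevation categories look for any occurrence after baseline, on a worst-case basis, and the Hy's-law plot uses maxima.

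For transfusion-impacted parameters, 5.7.13.1 and 5.7.13.2 use the same median step, but the grade is "set to the most frequent grade or worst grade if two grade have the same frequency".

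Two protocol provisions make same-day duplicates possible. On local laboratories, 13.6 says "they may also be utilized for analysis of samples collected for assessment of possible AEs". Section 13.9.5 says "Grade 3 and 4 clinically significant laboratory abnormalities should be confirmed by repeat testing".

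**The concern.** A median is a sensible way to get one value per day for a by-visit mean or a plot. It is the wrong input for a table meant to show the worst result. Laboratory abnormalities are part of the primary endpoint (SAP 3.2.1), and Grade 3 or 4 laboratory abnormalities are one of the five safety proportions named at the start of SAP Section 9.

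The grade step shows that the rule reaches these tables. A descriptive mean needs no toxicity grade, so attaching one to the median record only makes sense if that record feeds graded displays (SAP Table 7, tables 14.3.3.6 to 14.3.3.11).

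There is also a knock-on effect. The liver profile plots and the special liver listing in 9.2.2 are triggered by a Grade 3 or 4 result, so a subject whose grade was reduced could be missed there too. Elsewhere the SAP leans the other way: 5.7.11 gives an adverse event with missing severity the highest severity.

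**Working it through.** The plan states no figure to reproduce. The check is to apply 5.7.12 literally and compare it with taking the worst record.

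Inputs: the DMID grades for ALT in Protocol Appendix 1, in multiples of ULN. Grade 1 is 1.1 to <2.0, Grade 2 is 2.0 to <3.0, Grade 3 is 3.0 to 8.0 and Grade 4 is >8. The ALT values below are invented for illustration.

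| Same-day ALT (x ULN) | Value under 5.7.12 | Grade under 5.7.12 | Worst record |
|---|---|---|---|
| 2.6, 2.8, 3.6, same lab | median 2.8 | grades 2, 2, 3: Grade 2 | 3.6, Grade 3 |
| Central 2.9, local 3.2, outside South Africa | 2.9 (local dropped) | Grade 2 | 3.2, Grade 3 |
| 2.6, 3.2, same lab | (2.6 + 3.2)/2 = 2.9 | grades 2 and 3 tie: undefined | 3.2, Grade 3 |
| 2.5, 8.6, same lab | (2.5 + 8.6)/2 = 5.55 | grades 2 and 4 tie: undefined | 8.6, Grade 4 |

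In the first two rows, assume a baseline ALT below Grade 1 and no higher ALT on another date. The subject then enters the shift table as Grade 2 and is absent from the Grade 3 or 4 table (14.3.3.7). Rows three and four show the tie gap: two same-day records with different grades always tie. In row four the median lies in the Grade 3 range although neither record is Grade 3.

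As a conditional illustration, suppose a day has three same-lab records, each independently Grade 3 or higher with probability p. At least one such record occurs with probability 1 − (1 − p)³. The median reaches Grade 3 only if at least two do: 3p²(1 − p) + p³.

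| p | Any Grade ≥3 | Median Grade ≥3 | Share of such days lost |
|---|---|---|---|
| 0.1 | 27.1% | 2.8% | 1 − 0.028/0.271 = 90% |
| 0.3 | 65.7% | 21.6% | 1 − 0.216/0.657 = 67% |
| 0.5 | 87.5% | 50.0% | 1 − 0.500/0.875 = 43% |

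Both p and independence are assumptions. The table describes what happens given three same-day results; it says nothing about how often that occurs.

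**The case against.** The strongest reply is that the gap is narrow and partly answered by other text.

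- Section 9.2.1 speaks of any graded abnormality and of the worst grade, which can be read as drawing on all records. That reading is possible, but nothing in 9.2.1 sets 5.7.12 aside, whereas 9.2.2 says explicitly what enters. The text is ambiguous at best.
- Only results on the same date are touched. Protocol 13.9.5 does not ask for the repeat on the same day, and 13.9.5.2 would have an ALT elevation confirmed ideally inside 72 hours. Protocol 13.6 also lets a local laboratory replace the central one, and a lone local result is not dropped. All of this stands.
- Clinically significant findings are also recorded and graded as adverse events, and individual data are listed as measured (Protocol 13.6 and 14.3.2). This stands too: information is lost from the laboratory tables, not from the study report as a whole.

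Three stronger readings are tempting, and the documents do not support them.

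- A reader might infer that the rule removes cases from the liver fold-ULN and Hy's-law displays. Section 9.2.2 has its own worst-case rule, and Section 5 lets data-specific rules stand with their tables. For example, a local ALT of 9 x ULN against a same-day central 7.5 changes no 9.2.2 category: both exceed 1.5, 3 and 5, and neither exceeds 10. Both also count in the pooled Grade 3 or 4 table unless baseline was already Grade 3; only the split between the two grades moves.
- A reader might infer that same-day duplicates cluster on days when something is wrong. That is plausible, but the documents give no frequency.
- A reader might infer that 5.7.12 governs every table. SAP 9.2 sends hemoglobin and the other transfusion-impacted parameters to 5.7.13, which uses the same median and most-frequent-grade step but does resolve ties.

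**Conclusion.** The point holds for the treatment-emergent graded, Grade 3/4 and worst-post-baseline shift tables. As written, 5.7.12 can turn a Grade 3 or 4 result into a lower grade, can discard a same-day result from the non-preferred laboratory, and leaves the grade undefined when two same-day records differ. This rests on reading 5.7.12 as applying by default wherever a later section is silent, which its general wording and its grade step support.

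The number of subjects affected cannot be computed from the documents. It requires more than one result for a test on one date and no equally bad result on another date, so it may be small. For the liver fold-ULN and Hy's-law displays there is no demonstrated loss, only an unstated order of precedence. The change is worth making because these tables serve the primary endpoint and the repair is cheap, but the safety analysis does not fail without it.

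**What to change.** Amend the SAP as follows.

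1. Limit the same-day selection in 5.7.12 to by-visit descriptive summaries and plots.
2. In 9.2.1, derive treatment-emergent grades, Grade 3/4 counts and worst-grade shifts from all post-first-dose records, each graded against its own laboratory's reference range, taking the worst. Word this so that it also covers the parameters that 9.2 sends to 5.7.13.
3. State that 9.2.2 takes precedence over 5.7.12.
4. Where a by-visit grade is still needed, break ties to the worst grade, as 5.7.13 does.
5. Prespecify how South African central-laboratory results are handled. SAP 5.7.13.1 describes them as lacking reliability, so pooling every laboratory without qualification would bring doubtful values into the worst-case tables. One option is the local laboratory as primary for those sites, with a sensitivity display that adds the central results.

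The cost is a short SAP edit and a little more programming, with no new data. Counts of graded abnormalities may become slightly less favourable.
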